### **Secondary Objectives**

- Tolerability: Adverse experiences observed over the 7-21 days of protocol follow-up will be characterized in CTCAE v5.0. Frequency and severity of AEs according to body system and severity criteria will be described. In addition, frequency of grade 3 or 4 adverse events will be described separately. Causality will also be noted. Laboratory assessments will also be described according to the NCI CTCAE, V 5.0 criteria, with separate descriptions for grade 3 or 4 laboratory abnormalities. Clinically significant laboratory abnormalities will be described as well.
- Pharmacodynamics: Descriptive statistics, using means/ median, will be used to report drug effect on:
  - a) HK2 activity in resected tumor tissue
  - b) Concentration of downstream glycolysis metabolites in resected tumor tissue

- c) Tumor cell proliferation, cell death, and angiogenesis in resected tumor tissue
- d) Concentration vs time profile of lactate and pyruvate, based on MDC studies, in relation to the concentration vs time profile of posaconazole.

\*\* The above values will be compared to levels in the control arm.

### **Off Study Criteria**

Follow-up for this protocol will be considered complete when: (1) intraoperative pathology not consistent with glioma; (2) the patient dies; (3) the patient refuses posaconazole during the preoperative steady-state dosing period; (4) misses more than 3 doses; or (5) completes the 14 +/- 7 day follow-up after surgical resection of tumor. If a drug/ procedure-related complication has occurred, the patient will be clinically followed and managed accordingly until resolution.

Patients' disposition will be summarized in the following manner:

- The number and percentage of patients selected, included, completed, withdrawn and lost to follow-up will be summarized using descriptive statistics.
- Major protocol deviations will be summarized.
- The reason for withdrawal (adverse events, major protocol deviation, non-medical reason) will be summarized.

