### **3.3 Early Withdrawal of Subjects**

#### **3.3.1 Criteria for removal from study**

A participant should be withdrawn from the trial treatment if, in the opinion of the PI, it is medically necessary, or if it is the wish of the participant. If a participant does not return for a scheduled visit, every effort will be made to contact the participant. In any circumstance, every effort will be made to document participant outcome, if possible.

Participants should be removed from therapy if any of the following occurs:

- Adverse event: The occurrence of unacceptable toxicity indicating the need for cessation of treatment
- The physician feels it is in the best interest of the patient to stop treatment
- The participant desired to withdraw from further participation in the study in the absence of an investigator-determined medical need to withdraw. If a reason for withdrawal is given, it should be recorded in the case report form
- Protocol violation: The participant 's findings or conduct failed to meet the protocol entry criteria or failed to adhere to the protocol requirements (e.g. study drug compliance, returning for the specified number of visits)
- Participant is lost to follow-up. If a participant does not return for scheduled visits, every effort should be made to re-establish contact. In any circumstance, every effort should be made to document participant outcome, if possible

- Participant becomes pregnant
- Termination of the study

The reason and date of discontinuation are to be documented in the participant 's medical record and in the case report form. All participants who receive one or more doses of study treatment should be included in any safety analysis. The PI may discontinue the trial at any time. Reasons for early trial discontinuation may include, but are not limited to, unacceptable toxicity of study treatment, a request to discontinue the trial from a regulatory authority, or poor enrollment.

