#### **Microdialysis collection/monitoring**

After the imaging confirms proper placement of the MDC tip, the inlet tubing will be connected to a portable syringe pump to perfuse artificial CSF (Perfusion Fluid CNS, ref. no. P000151, CMA, Solna, Sweden) at a rate of 1.0  $\mu$ l/min. The inlet tubing of the catheter will be connected to a CMA 107 Microdialysis Pump (ref. no. P000127, CMA, Solna Sweden). A microvial will be connected at the end of the outlet tubing to collect perfusate.

Concurrently, a plastic microvial (Ref. No. P000001, CMA, Solna, Sweden) will be placed in the vial holder at the end of the outlet tubing to collect dialysate. This microvial can hold up to 200 $\mu$ L of fluid. It will need to be replaced with a new one every 3 hours. During daytime work week hours, trained research coordinators, in coordination with nursing team will collect dialysate and replace the microvials. At all other times, these tasks will be performed by the study PI, [name].

Dialysate sample collection will begin in the morning of postoperative day 1. If the participant was able to tolerate the AM dose of study drug (study drug group only), sample collection will begin immediately after drug administration. Otherwise, sample collection will begin within the same allotted time period (i.e. 8AM +/- 4 hours). For the control group, sample collection will be at 8 AM +/- 4 hours. The initial sample will be labeled as the 'Time 0' sample. Additional samples will be collected at 15 and 30 minutes, along with 1, 2, 4, 6, 8, and 24 hours after 'Time 0'.

Microvials containing the dialysate should be stored in an ultralow temperature freezer ( $\leq 70^{\circ}\text{C}$ ) until they can be batch analyzed by LC/MS/MS.

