##### Pharmacokinetics of delayed-release Posaconazole tablets:

When given orally in healthy volunteers, posaconazole delayed-release tablets are absorbed with a median Tmax of 4 to 5 hours. The elimination half-life of posaconazole has been estimated to vary between 15-35 hours [56]. Steady-state plasma concentrations are attained by Day 6 at the 300 mg dose (QD after BID loading dose at Day 1).

The absolute bioavailability of the oral delayed-release tablet is approximately 54% under fasted conditions. The Cmax and AUC of posaconazole following administration of posaconazole delayed-release tablets is increased 16% and 51%, respectively, when given with a high fat meal compared to a fasted state. In order to enhance the oral absorption of posaconazole and optimize plasma concentrations, posaconazole delayed-release tablets should be administered with food.

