### 8.2 Sample size determination

#### Design

This is an exploratory (pilot) study to assess whether posaconazole can penetrate brain tissue at sufficient enough levels to result in expected downstream biological effects on glycolysis and tumor cell survival. Five evaluable patients will be studied for this trial. The sample size justification is not based on statistical rationale but clinical affordability.

The following metrics will be used to define success and support the decision to proceed with advanced phase trials:

- Detection of  $\geq 5\mu\text{M}$  concentration of either drug in resected tumor in at least 2 of 5 patients in each arm – a value that is within the range needed to achieve efficacy for CNS fungal infections and to achieve 50% glioma tumor cell kill *in vitro* based on our prior published report (ref 58); AND
- Reduction in average lactate and pyruvate concentrations in both resected tumor and dialysate fluid (using MDCs) in the treated cohorts compared to controls; AND
- Steady concentration of lactate and pyruvate over 24 hours of monitoring with MDCs in control participants.

The rationale for the above is based on the notion that any tumor penetration by drug, with concomitant effect on glycolysis, warrants further in-depth analysis as our therapeutic options for these deadly tumors are currently very limited. Intra-tumoral drug concentration on the lower range would still be promising and warrant dose-escalation studies, as the currently selected dosing is based on anti-fungal regimens that are known to be safe. Phase II studies for assessing tumor response would be warranted if substantial tumor penetration together with expected biological effect is observed. A negative trial would nonetheless have value as it would serve as an efficient means of determining whether or not either of ketoconazole or posaconazole hold promise against GBMs, as part of a “fail early” approach to drug-development, while minimizing the human and financial cost investment.

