### **Study Population**

Only patients who are eligible and take posaconazole according to protocol specifications (study drug arm only) **and** have undergone successful MDC implantation will be considered evaluable and included in the study analysis. Otherwise, enrolled patients will be replaced. All eligible patients for whom analyzable dialysate samples were obtained for at least 7 of the 9 time points will be considered evaluable for the primary study endpoint. Patients who are not evaluable will be replaced.

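### Patients sampled without the postoperative day 1 dose are pooled into AUC0-24, and catheter placement does not wait for the same-day dosing check

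*Combined protocol and SAP*

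**What the plan says.** **Day 1 dose.** Under 7.2.1 and 7.2.5 the treated patient takes a dose on the morning of postoperative day 1, and dialysate sampling starts right after it. For a patient who did not tolerate that dose, 7.2.5 (Microdialysis collection/monitoring) adds: "Otherwise, sample collection will begin within the same allotted time period".

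**Who is analyzed.** Section 8.2 (Study Population) has two rules. A treated patient must "take posaconazole according to protocol specifications" and have a successfully implanted catheter, or be replaced. Eligible patients with analyzable dialysate "for at least 7 of the 9 time points will be considered evaluable for the primary study endpoint". The second sentence does not mention dosing.

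**Analysis.** Section 8.3 estimates AUC0-24 from whatever time points an evaluable patient has. It also describes brain concentration at steady state, and it summarizes AUC and Cmax across patients. It does not separate patients dosed at Time 0 from those who were not.

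**Catheter.** Section 7.2.3 lists a compliance and diary check on the day of surgery and records the time of that morning's dose. The intra-operative text then makes the research steps, including the catheter, depend on frozen-section confirmation of high-grade glioma.

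**Other dosing rules.** Section 3.3.1 allows removal of a patient who "failed to adhere to the protocol requirements (e.g. study drug compliance", without a threshold. The Off Study Criteria in 8.3 include a patient who "misses more than 3 doses". Section 18.2 allows a reduction to 200 mg after a grade 3-4 event.

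**The concern.** AUC0-24 is the primary outcome and is meant to describe the brain profile over a dosing interval at steady state. A patient who was not dosed at Time 0 contributes a 24-hour washout curve: no new peak, a lower AUC, and a level that is no longer steady. With five treated patients, one such curve moves the mean visibly, and the plan reports it under the same label. The plan foresees this case, because it writes a sampling path for it.

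The catheter issue concerns patients more than estimates. The resection is clinically indicated, but the catheter is there only for research. Section 10.0 lists bleeding, a 1% infection risk, and breakage that could need surgery. A catheter placed in a patient already known to fail 8.2's dosing condition carries those risks for data that will be replaced. Because 8.2 does not say which missed doses break the condition, a strict reader would replace a patient even for one early miss that hardly affects exposure.

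**Working it through.** **1. The plan's own figure.** Steady state at five half-lives: 5 × 26 h = 130 h and 5 × 31 h = 155 h. This reproduces the 130-155 h in 7.2.1.

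**2. Inputs.**
- Regimen: 300 mg twice on day 1, then 300 mg daily for 168-240 h before surgery (7.2.1).
- Mean half-life 26-31 h (7.2.1). Wider range from 7.4.1: "The elimination half-life of posaconazole has been estimated to vary between 15-35 hours".
- Tmax 4-5 h (7.4.1); 4.5 h used.
- Five evaluable treated patients (8.2).
- Assumed: one-compartment linear kinetics, and brain and tumor levels proportional to plasma. Section 2.3 itself calls plasma an unreliable guide to brain delivery, so the results are illustrative.

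**3. AUC0-24 without the day 1 dose.** Let r = 2^(−24/half-life), the share of drug left after one dosing interval. At steady state with immediate absorption, AUC0-24 without the dose divided by AUC0-24 with it equals r. The last column repeats this with first-order absorption set to Tmax 4.5 h.

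| Half-life | r (immediate absorption) | Ratio with Tmax 4.5 h |
|---|---|---|
| 26 h | 0.527 | 0.546-0.547 |
| 31 h | 0.585 | 0.601 |
| 15 h | 0.330 | 0.356 |
| 35 h | 0.622 | 0.635-0.636 |

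The range is 53-60% at 26-31 h and 33-64% at 15-35 h.

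**4. Effect on a mean of five.** With equal full-dose AUCs, one undosed patient lowers the mean by (1 − ratio)/5.
- 26-31 h: (1 − 0.601)/5 = 8.0% to (1 − 0.527)/5 = 9.5%.
- 15-35 h: (1 − 0.636)/5 = 7.3% to (1 − 0.330)/5 = 13.4%.

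**5. Why timing should define the dosing condition.** At steady state, the dose taken n days before surgery supplies a share r^n × (1 − r) of the level at tumor sampling. Missing only that dose leaves 1 − r^n(1 − r):
- n = 4 (96 h before): 1 − 0.527⁴ × 0.473 = 0.963 at 26 h; 1 − 0.585⁴ × 0.415 = 0.951 at 31 h.
- n = 5 (120 h before): 0.981 and 0.972.
- n = 1 (24 h before): 1 − 0.527 × 0.473 = 0.751; 1 − 0.585 × 0.415 = 0.757.
- n = 0 (surgery morning): r itself, 0.527 and 0.585.

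An isolated early miss keeps 95-98% of exposure. A missed surgery-morning dose keeps little more than half.

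**6. Dose reduction.** Under linear kinetics, steady state on 200 mg is 200/300 = 67% of the 300 mg level. Section 18.2 provides for this reduction, so such a patient can meet 8.2's condition and enter the same summary.

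**7. Catheter.** Set side by side, the diary check in 7.2.3 comes on the day of surgery, 8.2 makes evaluability depend on dosing, and the intra-operative text asks only for pathology before the catheter is placed. Nothing links the check to the placement.

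**The case against.** **The undosed AUC is a deliberate choice.** Section 7.2.5 provides for it, the 7-of-9 rule admits it, and 8.3 works with the time points available. This stands: the patient counts, and should. One could argue instead that 8.2's first rule excludes anyone who missed the day 1 dose. That would mean replacing a patient whose catheter is already in, so it is the worse reading. The gap is that a patient who counts is not reported apart.

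**The analysis is descriptive.** There is no test, median and range are allowed when variation is large, major deviations are summarized, and plasma is drawn at every dialysate time. An unusual patient would probably be noticed. This stands and keeps the point minor.

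**A tempting stronger reading.** A reader might infer that the off-study cap of three lets a patient with three misses just before surgery into AUC0-24 and the tumor criterion. With misses at 24, 48 and 72 h, the same model gives 52-55% of full exposure at tumor sampling. The documents do not support the inference. The cap sits in a list of events that complete follow-up, next to death and completed follow-up. Inclusion is set by 8.2, which asks for dosing as specified. Preoperative refusal (8.3) and poor compliance (3.3.1) are further routes out.

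**A false stop decision.** The documents do not support this either. Tumor is sampled before the day 1 dose, so that dose cannot change the 5 µM result. The criterion needs success only "in at least 2 of 5 patients in each arm", and 8.2 adds: "Intra-tumoral drug concentration on the lower range would still be promising and warrant dose-escalation studies".

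**Conclusion.** The concern holds in two limited parts. First, a patient without the day 1 dose is evaluable and is pooled with dosed patients in AUC0-24, Cmax and the steady-state summary. That patient's AUC0-24 is 40-47% lower at a half-life of 26-31 h, and the five-patient mean falls by 8.0-9.5%. Second, the catheter is not conditional on a dosing check the plan already makes, so a patient who must be replaced can still receive one.

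The sizes rest on linear one-compartment kinetics, steady state before surgery, brain tracking plasma, and similar AUCs across patients. Slower exchange between brain and plasma would make the day 1 effect smaller. The documents do not say how often a day 1 dose is not tolerated or a preoperative dose is missed, so the expected effect cannot be computed. The missing tolerance for missed doses in 8.2 is mainly a missing detail. Minor; a cheap improvement.

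**What to change.** 1. **Section 8.3.** State that patients sampled without the day 1 dose stay evaluable and are not replaced. Report their AUC0-24 and Cmax separately from patients dosed at Time 0, with the paired plasma values. Do the same for patients reduced to 200 mg. The day 1 dose should not become a condition of evaluability: by then the catheter is in, and each exclusion would mean another patient and another catheter.

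2. **Section 7.2.3.** Before a catheter is placed, require the Visit 3 diary check to confirm 8.2's dosing condition, in addition to pathology.

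3. **Section 8.2.** Say that the dosing condition turns on the last preoperative doses, including the surgery-morning dose, so that an isolated early miss does not lead to replacement. How many of the last doses to require is the sponsor's choice. The off-study cap can stay as it is.

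The cost is a few sentences; the diary, chart and plasma data are already collected. On the downside, the summary of dosed patients may rest on fewer than five, and an occasional patient will receive no catheter and be replaced.

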## **9.0 Data and Safety Monitoring Plan**

### **9.1 Periodic evaluation of data**

To monitor safety throughout the course of the study, every effort will be made to remain alert to possible AEs/SAEs. If an AE/SAE occurs, the first concern should be for the safety of the subject. If necessary, appropriate medical intervention will be provided. At the signing of the written consent form, each subject or his/her legally authorized representative and/or main caregiver must be given the names and telephone numbers of study site staff for reporting AEs/SAEs and medical emergencies. In this study, any AE/SAE experienced by the subject between the time of first dose of study treatment and 24 hours after the last dose will be recorded on the electronic case report form, regardless of the severity of the event or its relationship to study treatment. During study treatment and visit after 14 days, the research team will assess the subject for AEs and will record any new AEs/SAEs or updates to previously reported AEs on the electronic case report form.

### **9.2 Data that are reviewed**

Data reviewed are described below.

- Retrieved tumor sample:
  - Drug concentration
  - Hexokinase 2 enzyme activity assay
  - TUNEL staining for assessment of apoptosis
  - Glycolysis metabolites (lactate and pyruvate)
  - Immunohistochemistry – Ki67 staining for assessment of cell proliferation
- Blood and dialysate:
  - Drug concentration
  - Glycolysis metabolites (lactate and pyruvate)
- Clinical safety data:
  - Adverse events, as per NCI CTCAE v 5.0 criteria

### **9.3 Method of collection of safety information**

Safety information will be collected in the research database throughout the study. The safety of the study drug will be evaluated by clinical assessments and laboratory tests (see section 7.2).

#### **9.4 Frequency of data collection**

Data collection will occur as follows:

- Laboratory data:
  - Once – Resected tumor, blood samples, and dialysate samples will be analyzed in batch
- Clinical safety data:
  - Monitored at every study visit (please refer to schedule of events)

#### **9.5 Individuals reviewing the data**

The following individuals will review the data:

- [name] (PI)
- [name] (Co-investigator; Co-I)
- Additional research personnel as required

#### **9.6 Frequency of review of cumulative data**

Cumulative data will be reviewed once, upon conclusion of the study.

#### **9.7 Statistical tests**

For details, see the statistical section under 8.3.

#### **9.8 Suspension of research**

This is pilot study, but after periodic evaluation of study result and safety profile, the PI can terminate the research anytime based on outcomes of periodic safety monitoring and benefit/risk outcomes and will inform the IRB if such a decision is being made.

### **10.0 Risks**

#### **Risk of drug**

While this drug has never been tested specifically in the HGG population, it is an FDA-approved drug. The potential side effects are:

Common side effects (occurring in at least 1 in 100 patients) are:

- Headache
- Dizziness
- numbness or tingling;
- sleepiness
- feeling or being sick
- loss of appetite
- stomach pain
- diarrhea
- upset stomach
- nausea
- vomiting
- flatulence (excessive gas in the digestive tract)
- dry mouth
- abnormal liver function tests
- rash
- weakness
- tiredness
- a decrease in white blood cells (that can increase the risk of infections)
- fever

- abnormal amounts of salts in the blood

#### Infrequent

- Liver problems, including liver failure, with symptoms such as:
  - dark colored urine
  - pale stools
  - yellowing of the skin and eyes
  - abdominal pain
  - nausea
  - vomiting

#### Uncommon

- Heart problems such as very slow, fast or irregular heartbeat

#### Rare

- Severe allergic reaction with symptoms such as
- severe skin blistering
- peeling rash
- swollen lips, mouth and throat
- difficulty in breathing

### **Risks of microdialysis**

Microdialysis is an invasive surgical procedure with a small risk of bleeding at the site of insertion and discomfort for the patient. Removal of the catheter can result in minor discomfort as well. There is a chance that the catheter may break or get stuck in the brain that would require surgical intervention to remove it.

There is also a small risk of infection (1%), but pre-operative antibiotics are used to reduce the risk. However, this is a small device and it is removed early postoperatively, similar to other surgical drains placed postoperatively. There is also a very small possibility of bleeding along the catheter tip.

### **Risks of venipuncture**

The discomfort associated with removing blood by venipuncture (by a needle from a vein) is a slight pinch or pin prick when the sterile needle enters the skin. The risks include mild discomfort and/or a black and blue mark at the site of puncture. Less common risks include a small blood clot, infection or bleeding at the puncture site, and on rare occasions fainting during the procedure.

### **Risks of electrocardiogram (ECG):**

The patches that the study staff will stick to your chest and other areas of your body to monitor your heart may irritate your skin and cause itching and redness. The study staff might need to shave your body hair so that they can stick the pads to your skin. The shaving may cause some irritation (depending on the tools and soap used); also, a local allergic reaction could occur. When the sticky patches are removed, it might sting for a few seconds. The test itself is painless.

### **Reproductive risks**

The class of drugs, azoles, which the study drug is part of, can cause birth defects. There is only limited information regarding their effect on infants of breastfeeding mothers. For this reason, all women of childbearing potential MUST have a negative pregnancy test.

The study doctor will discuss methods with participants to ensure that they do not become pregnant or father a baby during the study. Women should not breastfeed a baby while taking study treatment and for 30 days after the last dose because the drug used in this study might be present in breast milk and could be harmful to a baby.

